6.4.4 Laboratory safety assessments

Blood and urine samples for determination of clinical chemistry, hematology, coagulation and urinalysis will be taken at the visits as indicated in the Study Plan (Table 2 and Table 3). Blood samples for laboratory safery assessments should be collected after a 8-hour fast (no food or drink, except water).

Blood and urine samples for safety assessment will be collected at the following times:

- Screening.
- Weekly during Cycle 1: Pre-dose on Day 1, Day 8 and Day 15.
- On Day 1 of each subsequent Cycle: Pre-dose.
- Discontinuation visit.

The date and time of each collection will be recorded in the appropriate CRF.

The timing of blood samples may be altered depending on the emerging PK and safety profile. Additional sampling times may be added if indicated by the emerging data.

Laboratory values that meet the criteria for CTCAE Grade 3 or have changed significantly from baseline and are considered to be of clinical concern will be repeated/confirmed within 7 days and followed up as appropriate.

The following laboratory variables will be measured during study:

Serum Chemistries	Hematology	Coagulation	Urinalysis
Albumin	Hemoglobin	PT	U-Glucose
Alkaline phosphatase	Hematocrit	PTT or aPTT	U-Protein
ALT	Platelet count	INR	U-Blood**
AST	Red blood cell count		U-Leucocytes***
Bicarbonate	White blood cell count		
Blood urea nitrogen	Differential cell count:		
Calcium	Basophils		
Chloride	Eosinophils		
Creatinine	 Lymphocytes (absolute) 		
CRP	Monocytes		
Glucose	 Neutrophils (absolute) 		
LDH	Reticulocytes		
NT-pro BNP		·	1
Phosphate			
Potassium		ı	
Sodium		ł	
Total bilirubin		Ì	
Total serum protein			
Troponin T* or Troponin I			
Total cholesterol			
Triglyceride			
HDL-C			
LDL-C			
Apo-A			
Apo-B			
Creatine Kinase			

aPTT = activated partial thromboplastin time; INR = international normalized ratio; LDH = lactate dehydrogenase; PT = prothrombin time; PTT = partial thromboplastin time.

In addition, sample will be collected from all females of child-bearing potential at screening, before the first dose, and at treatment discontinuation for a pregnancy test. In case a patient shows an AST

^{*}High sensitivity cTnT (hs-cTnT) assay (if applicable) is recommended.

^{**} In case of positive urine blood test, assessment of red blood cell count in urine should be performed.

^{***} In case of positive urine leucocytes test, assessment of leucocytes count in urine should be performed.

or ALT \geq 3 × ULN or total bilirubin \geq 2 × ULN please refer to Appendix III. HY's Law 'Actions required in cases of combined increase of aminotransferase and total bilirubin – Hy's Law' for further instructions.

6.4.5 Other safety assessments

Echocardiogram/MUGA Scan

Echocardiogram or MUGA scan to assess LVEF will be conducted at screening (prior to first dose of AZD4205), Cycle 3 Day 1, then every 12 weeks for the rest of cycle. Additional Echocardiogram or MUGA scan will be performed whenever necessary as clinically indicated throughout the study.

The modality of the cardiac function assessments must be consistent within a patient i.e. if echocardiogram is used for the screening assessment then echocardiogram should also be used for subsequent scans if required. The patients should also be examined using the same machine and operator whenever possible, and a quantitative measurements should be taken. Recommendations include having complete high quantity standardized 2-D with Doppler echocardiographic examinations performed by an experienced sonographer and include evaluation of both systolic and diastolic left ventricular function. Ejection fraction determinations should be determined quantitatively based on bi-plane measurements of end diastolic and end systolic left ventricular volumes.

An asymptomatic LVEF decrease to < 40% or LVEF [40-54%] and LVEF decrease \ge 10% from baseline or any symptomatic LVEF decrease are the dose interruption criteria. Any symptomatic decrease in LVEF will prompt the discontinuation of the treatment and a cardiac consultation.

Pulmonary function tests (PFTs)

Signs and symptoms (cough, short breath and pyrexia, etc) including auscultation for lung field will be checked at each visit.

PFTs (including spirometry and DLCO) will be performed at screening, Cycle 3 Day 1 and then every 6 weeks and whenever clinically indicated.

HRCT scan will be performed when clinically indicated (see below, details could be found in Appendix VII. Guidance for the Safety Monitering and Management of Adverse Events):

- If new or worsening pulmonary symptoms (e.g., dyspnea) or radiological abnormality suggestive of interstitial lung disease on CT scan or decrease in lung function tests (DLCO decrease ≥ 15%) is observed, the study treatment dosing should be interrupted and a full diagnostic workup (including chest X-Ray with PA and lateral view, cardiac, infectious and hematological workups) will be performed. A full diagnostic workup is strongly recommended to exclude alternative causes such as infection, disease progression and cardiac causes. Alternative clinical diagnosis will be managed according to local practice.
- If other causes of respiratory changes have been excluded an HRCT scan should be performed. If a diagnosis of drug-induced pneumonitis is confirmed, study treatment

should be permanently discontinued. In the absence of a diagnosis of drug-induced pneumonitis, study treatment may be restarted.

Hepatitis screen, HIV screen

All patients will be screened for Hepatitis B surface antigen (HBsAg) and Hepatitis B core antibody (HBcAb). Both HBsAg and HBcAb should be negative for eligibility.

Screening for Hepatitis C will be based on HCV antibodies.

Evaluation for HIV seropositivity will be performed, and, if positive, confirmation by a second technique available at the laboratory site, e.g. Western blot.

Appropriate counselling will be made available by the Investigator in the event of a positive finding. Notification of regional and/or national authorities, if required by law, will be the responsibility of the Investigator.

Ophthalmic examinations

Ophthalmic examinations by specialist should be performed for all patients at baseline, Cycle 3 and then every 3 cycles (approximately every 2 months) after enrolment. The recommended ophthalmic examinations include visual acuity (corrected), intraocular pressure, slit lamp examination, and dilated ophthalmoscopy. For the grading and clinical management of ocular adverse events, refer to Appendix VII.

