5.2.2 Potential risks

Non-clinical toxicity studies of AZD4205 in rats and dogs and safety pharmacology experiments have been summarized in Section 2.3 of this protocol, which may indicate the potential adverse effects of AZD4205 in human. Further detailed information of non-clinical toxicity findings is available in the Investigator Brochure. The monitoring and management of the potential adverse effects of using AZD4205 is discussed below.

Cardiovascular effects

Patients who have unstable cardiac conditions and risk factors for QT prolongations will be excluded from participation in this study (detailed exclusion criteria are listed in Section 4.2). Concomitant use of regular medications that may prolong the QT interval will be restricted whenever feasible (See Appendix II), but patients may receive any medication that is clinically indicated for the treatment of AEs. Electrolyte and vital sign assessments, including pulse rate and blood pressure, will be monitored regularly throughout the study (See Section 6.1). Twelve lead ECG will be conducted throughout the study to monitor any

change of QT interval. Confirmed QTc prolongation (> 500 msec absolute or > 60 msec above baseline) is the dose interruption criteria (See Section 6.4.3). The investigator or designated physician will review each ECG prior to discharge from the clinic and may refer to a local cardiologist if appropriate for immediate management of the patients. A paper copy should be filed in the patient's medical records. If an abnormal ECG finding at screening or baseline is considered to be clinically significant by the investigator, it should be reported as a concurrent condition. An Echocardiogram or MUGA scan to assess LVEF will be performed at screening prior to first dose of AZD4205 to evaluate any pre-existing cardiac abnormality, followed by Cycle 3 Day 1, and then every 12 weeks, and wherever and whenever necessary as clinically indicated throughout the study. An asymptomatic LVEF decrease to < 40% or LVEF [40-54%] and LVEF decrease ≥ 10% from baseline or any symptomatic LVEF decrease are the dose interruption criteria (See Section 6.4.5 and Appendix VII). Both high sensitive troponin T testing and NT-pro BNP will be performed at screening, baseline and each subsequent cycle.

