- and symptoms associated with the abnormal finding should be reported as the AE with the ECG abnormality given as explanatory information.
- Management of QTc prolongation: A QTcF > 500 ms is an independent criterion for individual pro-arrhythmic risk. Any QTcF > 500 ms should trigger a repeat ECG timepoint in 5-10 min to confirm the finding. If confirmed, patient will be withdrawn from study Patients experiencing QTc interval prolongation with signs/symptoms of serious arrhythmia will not be permitted to restart study treatment.

Safety monitoring with Echocardiogram/MuGA:

- The modality of the cardiac function assessments must be consistent within a patient i.e. if echocardiogram is used for the screening assessment then echocardiogram should also be used for subsequent scans.
- The patients should also be examined using the same machine and operator whenever
 possible, and quantitative measurements should be taken. Recommendations include having
 complete high quality standardized 2-D with Doppler echocardiographic examinations
 performed by an experienced sonographer and include evaluation of both systolic and
 diastolic left ventricular function.
- Ejection fraction determinations should be determined quantitatively based on bi-plane measurements of end diastolic and end systolic left ventricular volumes.
- Any symptomatic decrease in LVEF will prompt the discontinuation of the treatment and a cardiac consultation.
- Below table is the reference for the management of asymptomatic decrease of LVEF:

Absolute EF	Decrease from Baseline <10%	Decrease from Baseline 10-15%	Decrease from Baseline >15%
55% or above	Continue	Continue	Interruption*. ECHO/MUGA in 3 weeks. If value back to baseline, consider dose resumption.
54-40%	Continue	Interruption. Cardiac consultation. ECHO/MuGA in 3 weeks. If LVEF above 55% consider dose resumption	Discontinue. Cardiac consultation
Below 40%	Interruption. Cardiac consultation	Discontinue. Cardiac consultation	Discontinue. Cardiac consultation

Footnote: *A subject with EF decreasing by > 15% and remaining > 55% would have to start from > 70%, i.e. a very high normal. Hypovolemia, hyperthyroidism and hypertrophic/constrictive/significant restrictive cardiomyopathy should be considered and ruled out.

Troponin and NT-pro BNP

- Both high sensitivity troponin T testing (TnT or hs-TnT) and NT-pro BNP will be performed.

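### The protocol gives two actions, interrupt and discontinue, for the same LVEF decrease in three situations, and states no rule for choosing between them

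*Protocol*

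**What the plan says.** LVEF is measured by echocardiogram or MUGA at screening, at Cycle 3 Day 1 and then every 12 weeks. Three places in the protocol say what to do when it falls.

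- **Section 6.4.5.** The asymptomatic rule begins "An asymptomatic LVEF decrease to < 40% or LVEF [40-54%] and LVEF decrease" and sets that decrease at 10% or more from baseline. The same sentence ends "or any symptomatic LVEF decrease are the dose interruption criteria". The sentence after it reads "Any symptomatic decrease in LVEF will prompt the discontinuation of the treatment and a cardiac consultation".
- **Section 5.2.2, cardiovascular effects.** It repeats only the interruption rule and points to the other two places: "any symptomatic LVEF decrease are the dose interruption criteria (See Section 6.4.5 and Appendix VII".
- **Appendix VII.** It repeats the discontinuation sentence for symptomatic decreases. It then gives a grid of absolute LVEF against size of decrease, introduced by "Below table is the reference for the management of asymptomatic decrease of LVEF". Some cells are interruptions with a route back to dosing, for example "Interruption. Cardiac consultation. ECHO/MuGA in 3 weeks. If LVEF above 55% consider dose resumption". Others read "Discontinue. Cardiac consultation".

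Table 1 in section 5.1.3.1, the main dose-modification table, has no LVEF row. No order of precedence between the body text and the appendix is stated.

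**The concern.** An investigator with a symptomatic LVEF decrease finds two actions in consecutive sentences of one section. For an asymptomatic decrease, the action depends on whether the investigator stays in the body text or follows the cross-reference to Appendix VII.

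Two things are at stake. The first is patient management: interruption leaves a return to dosing open, whereas section 5.3.1 says permanently discontinued medication is not restarted. The second is the safety data. SAP section 5.7.1 tabulates TEAEs leading to interruption and TEAEs leading to discontinuation separately, so the same cardiac finding could appear in different tables at different sites. The discontinuation count also enters the Part B monitoring rule in protocol section 5.1.2, which calls an ad-hoc SRC meeting once TEAE-related discontinuation or death reaches 19.7% after at least 20 patients are enrolled.

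**Working it through.** **Inputs.** The LVEF rules in protocol sections 5.2.2 and 6.4.5; the Appendix VII grid and its footnote; the entry requirement of LVEF at least 55% (section 4.1, criterion 9); the Part B trigger (section 5.1.2).

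**Step 1: scale of the decrease.** The Appendix VII footnote reads "A subject with EF decreasing by > 15% and remaining > 55% would have to start from > 70" (per cent). On absolute points, 55 + 15 = 70, which reproduces the footnote. A relative 15% fall would give 55 / 0.85 = 64.7, which does not. The table therefore works in absolute LVEF points.

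**Step 2: the rules side by side.**

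| Finding | Sections 5.2.2 and 6.4.5 | Appendix VII | Agree? |
|---|---|---|---|
| Symptomatic, any decrease | Interrupt (5.2.2 and 6.4.5); discontinue (next sentence of 6.4.5) | Discontinue | No |
| Asymptomatic, 40-54%, decrease above 15 | Interrupt | Discontinue | No |
| Asymptomatic, below 40%, decrease 10 or more | Interrupt | Discontinue | No |
| Asymptomatic, below 40%, decrease under 10 | Interrupt | Interrupt | Yes |
| Asymptomatic, 40-54%, decrease 10-15 | Interrupt | Interrupt | Yes |
| Asymptomatic, 40-54%, decrease under 10 | Not listed | Continue | Yes |
| Asymptomatic, 55% or above, decrease above 15 | Not listed | Interrupt | Gap |
| Asymptomatic, 55% or above, decrease 15 or less | Not listed | Continue | Yes |

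**Step 3: which rows an eligible patient can reach.** With a baseline of at least 55, a value below 40 means a fall of more than 55 - 40 = 15 points. On the relative scale the fall is more than 15 / 55 = 27.3%, so the result does not depend on the scale. The one cell below 40% where the two sources agree cannot be reached from an eligible baseline. Every eligible patient with asymptomatic LVEF below 40% is told to interrupt by the body text and to discontinue by the table.

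**Step 4: check by enumeration.** Take whole-number baselines from 55 to 80 and all lower on-study values down to 15.

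- Below 40%: 26 baselines x 25 values (15 to 39) = 650 combinations, and all 650 conflict on either scale.
- 40-54% with a decrease above 15 points: baselines 56 to 70 give 1 + 2 + ... + 15 = 120, and baselines 71 to 80 give 10 x 15 = 150. The total is 270, and all 270 conflict. On the relative scale it is 350 of 350.
- 40-54% with a decrease of 10-15 points: 75 combinations (25 on the relative scale), none in conflict.
- 55% or above with a decrease above 15 points: 55 combinations (114 on the relative scale) that Appendix VII interrupts and the body text does not list.

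These are counts of grid points. They say nothing about how often patients would fall there.

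**Step 5: sensitivity of the Part B trigger.** With 20 patients enrolled, 3 / 20 = 15.0% is below 19.7% and 4 / 20 = 20.0% is above it. At that size, one event recorded as an interruption instead of a discontinuation can decide whether the meeting is called. No LVEF event rate is given, so the chance of this cannot be computed.

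**The case against.** The best defence is that the two statements are sequential: interruption means stopping the drug at once, and discontinuation is what may follow. Table 1 gives this some support. Its trigger column is headed as toxicities needing immediate interruption, yet several of its rows carry permanent discontinuation as the plan. In addition, section 5.2.2 refers to Appendix VII, whose grid is labelled the reference for asymptomatic decreases, and the LVEF text never calls the discontinuation permanent.

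Part of this stands. Every discontinue cell in Appendix VII lies inside the body text's interruption bands, so a site following either source stops dosing. The ambiguity is about restarting, not about continuing to treat. The row at 55% or above is an omission from the body text and not a contradiction. The 19.7% figure prompts a review and not an automatic halt, section 5.1.3.1 allows deviations on clinical judgement, and the primary ORR analysis is not directly affected.

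The sequential reading itself does not stand, because no passage states it. The Appendix VII grid uses interruption and discontinuation as alternative entries and mentions resumption only under interruption. Calling the grid a reference does not place it above the body text, and it covers only asymptomatic decreases, so it cannot settle the consecutive symptomatic sentences in 6.4.5. Discretion to deviate presupposes a single rule to deviate from.

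**Conclusion.** The concern holds. Three situations carry two different actions: any symptomatic decrease; asymptomatic LVEF 40-54% with a decrease above 15 points; and asymptomatic LVEF below 40% with a decrease of 10 points or more. For patients who meet the entry criterion, the third covers every asymptomatic value below 40%. There is also one gap, at 55% or above with a decrease above 15 points.

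This rests on reading interruption and discontinuation as distinct actions, as the Appendix VII grid does, and on the absence of any stated precedence. The practical effect is on whether a patient may resume treatment and on how the event is counted. The number of patients affected cannot be derived from the documents. It should be corrected because it concerns a monitored cardiac risk. No position is taken here on which action is right.

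**What to change.** Replace the three statements with one LVEF action table, and have sections 5.2.2 and 6.4.5 cite it without restating thresholds. Each combination of symptoms, absolute LVEF and decrease from baseline should map to exactly one action. The table should:

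- state that the decrease is in absolute LVEF points;
- say whether discontinuation is permanent and, where interruption applies, what governs resumption;
- cover LVEF of 55% or above with a decrease above 15 points;
- be cited from Table 1.

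The sponsor's clinical team must decide the action in each cell.

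When this is done, the LVEF categories in SAP section 5.7.5 could be aligned with the agreed cut-points. They now split absolute LVEF at 50%, 40% and 20%, and the decrease at 10% and 20%, so the summary table cannot isolate the protocol's 55% and 15% boundaries. The individual listings can.

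The cost is protocol wording and, if taken up, a small SAP table change. No extra assessment or patient is needed.

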6.4.6 Safety follow-up

An end of study treatment assessment will be performed at the time investigational product is permanently discontinued (see Table 2 and Table 3).

In addition, a 28-day follow-up should be made by telephone contact after 28 days (± 7 days) following the discontinuation of the study treatment to collect new AEs and follow up on any ongoing AEs and concomitant medications (including any subsequent cancer therapy). Refer to section 6.5.3 for full details on AE recordings during follow-up.

6.5 Adverse events

The Principal Investigator is responsible for ensuring that all staff involved in the study is familiar with the content of this section.

6.5.1 Definition of adverse events

Any untoward medical occurrence in a patient or clinical investigation patient administered a pharmaceutical product and which does not necessarily have to have a causal relationship with this treatment. An adverse event (AE) can therefore be any unfavorable and unintended sign (including an abnormal laboratory finding, for example), symptom, or disease temporally associated with the use of a medicinal product, whether or not considered related to the medicinal product.

Any deterioration of the disease under study and associated symptoms or findings should not be regarded as an adverse event as far as the deterioration can be anticipated.

The term adverse event is used generally to include any AE whether serious or non-serious.

6.5.2 Definitions of serious adverse events

A serious adverse event (SAE) is an AE occurring during any study phase (i.e., screen, treatment, washout, and follow-up), that fulfils one or more of the following criteria:

- Results in death
- Is immediately life-threatening
- Requires in-patient hospitalization or prolongation of existing hospitalization
- Results in persistent or significant disability/ incapacity or substantial disruption of the ability to conduct normal life functions
- Is or results in a congenital abnormality or birth defect
- Is an important medical event that may jeopardize the patient and may require medical intervention to prevent one of the outcomes listed above.

For further guidance on the definition of a SAE, see Appendix IV of this Clinical Study Protocol.

6.5.3 Recording of adverse events

Time period for collection of adverse events

AEs will be collected and recorded in eCRF from first dosing of AZD4205 until the end of the follow up period. The follow-up period is defined as 28 days (± 7 days) after study treatment is discontinued. However, SAE should be collected and recorded in eCRF from ICF signing to the end of defined follow-up period (see Table 5).

Table 5 Summary of recording and follow-up of adverse events

	Consent to Randomization/first dosing	Until defined Follow up Visit (safety follow-up period)	Post Follow-up visit but prior to progression (if applicable)
Record all new AEs in CRF	No*	Yes	No
Record all ongoing AEs in CRF	No	Yes	No**
Record all study procedure related new SAEs in CRF	Yes	Yes	No***

^{*} Adverse events prior to the first dosing but worsening post the first doing should be recorded in eCRF as new AEs.

** All ongoing AEs/SAEs post safety follow-up period will be followed by investigator as long as medically indicated, but without further collection in eCRF.

After the final database lock, there may be some patients remaining on study treatment. For these patients who are continuing to receive AZD4205, Sponsor will collect information (during the treatment period and for 28 +/- 7 days after last dose) on SAEs, deaths (including those due to disease progression), discontinuation due to AEs/SAEs and drug accountability only.

^{***} New emerging SAEs post follow-up period including death should not be collected in eCRF, but still need to be reported to Dizal in the condition of causality with study procedure judged by investigator.

Follow-up of unresolved adverse events

Sponsor retains the right to request additional information for any patient with ongoing AE(s) at the end of the study, if judged necessary.

If an investigator learns of any SAEs, including death, at any time after a patient has completed the study and he/she considers there is a reasonable possibility that the event is related to AZD4205, the investigator should notify Sponsor.

Variables

The following variables will be collected for each AE:

- AE diagnosis/description
- The date when the AE started, stopped and intensity changed
- CTCAE grade (version 5.0); for the grading of specific ocular AEs, refer to Appendix VII (Table 18)
- Whether the AE is serious or not
- Investigator causality rating against the investigational product (yes or no)
- Action taken with regard to investigational product
- Outcome
- For SAEs other variables will be collected including treatment given for the event.

It is important to distinguish between serious and severe AEs. Severity is a measure of intensity whereas seriousness is defined by the criteria in Section 6.5.2. An AE of severe intensity need not necessarily be considered serious. For example, nausea that persists for several hours may be considered severe nausea, but not a SAE. On the other hand, a stroke that results in only a limited degree of disability may be considered a mild stroke but would be a SAE.

The grading scales found in the current National Cancer Institute CTCAE version will be utilized for all events with an assigned CTCAE grading. For those events without assigned CTCAE grades, the recommendation in the CTCAE criteria that converts mild, moderate and severe events into CTCAE grades should be used. A copy of the current CTCAE version can be downloaded from the Cancer Therapy Evaluation Program website (http://ctep.cancer.gov).

Causality collection

The investigator will assess causal relationship between investigational product and each adverse event, and answer 'yes' or 'no' to the question: 'Do you consider that there is a reasonable possibility that the event may have been caused by the investigational product?'

For SAEs causal relationship will also be assessed for other medication and study procedure. Note that for SAEs that could be associated with any study procedure the causal relationship is implied as 'yes'.

A guide to the interpretation of the causality question is found in Appendix IV of this Clinical Study Protocol.

Adverse events based on signs and symptoms

All AEs spontaneously reported by the patient or care provider or reported in response to the open question from the study personnel: 'Have you had any health problems since the previous visit/you were last asked?', or revealed by observation will be collected and recorded in the CRF. When collecting AEs, the recording of diagnoses is preferred (when possible) other than recording of a list of signs and symptoms. However, if a diagnosis is known and there are other signs or symptoms that are not generally part of the diagnosis, the diagnosis and each sign or symptom will be recorded separately.

Adverse events based on examinations and tests

The criteria for determining whether an abnormal examination finding, or laboratory parameter should be reported as an adverse event are as follows:

- Abnormal examination finding or laboratory result is accompanied with symptoms, and/or
- Abnormal examination finding or laboratory result requires or medical/surgical intervention, and/or
- Abnormal examination finding or laboratory result leads to a change in study dosing or discontinuation from the study, additional concomitant drug treatment, or other therapy, and/or
- Abnormal examination finding or laboratory result is considered to be an adverse event by the investigator or sponsor.

Abnormal examination finding or laboratory result which meets criteria above should be considered as clinically significant. Purely repeating an abnormal test, in the absence of any of the above conditions, is not considered an adverse event.

If an abnormal examination finding or laboratory parameter is associated with clinical signs and symptoms, the sign or symptom (preferably the diagnosis) will be reported as an AE and the associated laboratory result or other finding will be considered as additional information. If an abnormal examination finding or laboratory parameter is a sign of a disease or syndrome, only the diagnosis should be recorded as AE in CRF (e.g. both AST and ALT increase and reach AE criteria based on CTCAE, the AE term in CRF should be recorded as one AE of increased liver enzyme). Wherever possible the reporting investigator uses the clinical, rather than the laboratory term (e.g., anemia versus low hemoglobin value).

Disease progression

Disease progression can be considered as a worsening of a patient's condition attributable to the disease for which the investigational product is being studied. It may be an increase in the severity of the disease under study and/or increases in the symptoms of the disease (symptomatic progression). The development of new, or progression of existing metastasis to the primary cancer under study should be considered as radiological disease progression and not an AE. Events that

are unequivocally due to symptomatic or radiological disease progression should not be reported as AEs during the study.

New cancers

The development of a new cancer should be regarded as an AE and will generally meet at least one of the serious criteria. New cancers are those that are not the primary reason for the administration of the study treatment and have been identified after the patient's inclusion in this study. They do not include metastases of the original cancer.

Hy's Law

Cases where a patient shows an AST or $ALT \ge 3 \times ULN$ and total bilirubin $\ge 2 \times ULN$ may need to be reported as SAEs. Prompt reporting of cases meeting Hy's law criteria (via the SAE expedited reporting system) is required for compliance with regulatory guidelines. The investigator is responsible for, without delay, determining whether a patient meets potential Hy's law criteria. Details of identification of potential Hy's law cases and actions to take are detailed in Appendix III. HY's Law.

Handling of deaths

All deaths that occur during the study, or within the follow-up period after the administration of the last dose of investigational product, should be reported as follows:

- Death, which is unequivocally due to disease progression, should be communicated to the study monitor at the next monitoring visit and should be documented in the CRF module, but should not be reported as a SAE during the study.
- Where death is not clearly due to disease progression of the disease under study the AE causing the death should be reported to the study monitor as an SAE within 24 hours. The report should contain a comment regarding the co-involvement of progression of disease, if appropriate, and should assign a single primary cause of death together with any contributory causes.
- Deaths with an unknown cause should always be reported as a SAE but every effort should be
 made to establish a cause of death. A post-mortem may be helpful in the assessment of the
 cause of death, and if performed a copy of the post-mortem results (with translation of
 important parts into English) should be reported in an expedited fashion to Sponsor
 representative within the usual timeframes.

